10.6 Efficacy Subgroup Analysis

The percentage of ITT subjects with SVR₁₂ will be calculated, as will the corresponding two-sided 95% Wilson score confidence intervals for the following subgroups:

- HCV genotype (1, 2, 3, 4, 5, or 6) and available subtype (as defined in Section 10.8);
- Prior HCV treatment history (treatment-naïve or treatment-experienced);
 - For treatment-experienced subjects, type of previous regimen (IFN- or SOF-based);
 - For treatment-experienced subjects, occurrence of prior HCV treatment relative to renal or liver transplant (pre-transplant or post-transplant);
- Type of organ transplant (liver or kidney);
- Type of immunosuppressant medications (Tacrolimus, Cyclosporine, or other);
- IL28B genotype (CC or non-CC);
- Sex (male or female);
- Age (< 65 or \ge 65 years) and (< 75 or \ge 75 years);
- Race (White, Black/African-American, Asian, or other) and (black or non-black);
- Ethnicity (Hispanic or Latino, Not Hispanic or Latino);
- Baseline BMI (< 30, or \geq 30 kg/m²);
- Baseline HCV RNA level (< 1,000,000 or ≥ 1,000,000 IU/mL) and (< 6,000,000, or ≥ 6,000,000 IU/mL);
- Baseline fibrosis stage (equivalent to Metavir F0 F1, F2, F3, or F4 [if applicable]);
- Baseline platelet count (< 90 or \ge 90 × 10⁹/L);

- Baseline albumin (< 35 or \geq 35 g/L);
- Baseline creatinine clearance ($< 60, \ge 60$ to $< 90, \ge 90$ mL/min);
- Baseline eGFR (< $60, \ge 60$ to < $90, \ge 90$ mL/min/1.73 m²);
- Geographic region (North America, Europe, Rest of world);
- Country (as appropriate);
- History of diabetes (yes/no);
- Former injection drug user (yes, within last 12 months; yes, more than 12 months ago; or no);
- Subject on stable opiate substitution (yes/no);
- Presence of baseline resistance-associated variants (any NS3/4A variant [yes/no]; any NS5A variant [yes/no]; any NS3/4A and any NS5A variant [yes/no], any NS3/4A or any NS5A variant [yes/no]), and (NS3/4A variant only, NS5A variant only, both NS3/4A and NS5A, or none);
- Concomitant use of Proton Pump Inhibitors (PPIs) (yes/no).

The 2-sided 95% Wilson score confidence interval will be produced if there are at least 10 subjects in the subgroup.

For the subgroup analyses, the presence of baseline resistance-associated variants as listed above are defined in Section 10.8.1; this subgroup analysis will be performed in the mITT-GT-VF population.

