5.1.1.1 Retest/Rescreening

Subjects who at Screening have any of the following are not eligible to rescreen or retest:

- A positive Hepatitis B surface antigen (HBsAg);
- A positive HIV-1 Ab test;
- HCV genotype indicating co-infection with more than one HCV genotype;
- A positive serum pregnancy test (if female).

Otherwise, subjects may be retested or rescreened only once before requiring approval from the Primary Therapeutic Area Medical Director to rescreen again.

Retesting:

Subjects who have exclusionary laboratory parameter(s) per Exclusion Criterion 9, Section 5.2.2 are allowed to retest on the related panel(s) (e.g., exclusionary ALT requires a repeat chemistry panel) within the same screening period and must meet all other eligibility laboratory criteria on the panel that is repeated. If the retest result(s) are also exclusionary, the subject may only be rescreened or retested again with approval from the Primary Therapeutic Area Medical Director.

Rescreening:

Subjects that exceed the initial 42-day screening period should be rescreened for all laboratory and eligibility criteria, not just those that were exclusionary at the first screening attempt (with the exception of HIV, HBV, HCV genotype and subtype, follicle stimulating hormone (FSH), which do not need to be repeated). The FibroScan and liver biopsy do not need to be repeated for rescreened subjects provided that the date of the liver biopsy is within 6 months of the rescreening date and the FibroScan is within 3 months of the rescreening date (Section 5.1.1).

The Primary Therapeutic Area Medical Director should be contacted for approval prior to rescreening. Subjects that are beyond the initial 42-day screening period may still be allowed to enroll within a reasonable time period if they continue to meet all eligibility

criteria and have received approval by the Primary Therapeutic Area Medical Director. If rescreened, the 42 day screening period restarts, and subjects retain their initial subject number.

For subjects who rescreen and still do not meet the study eligibility criteria upon retest/rescreen, the site personnel must register the subject as a screen failure in both IRT and EDC systems.

5.1.2 **Treatment Period**

[figure not shown]

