A subject will not be eligible for study participation if he/she meets any of the following criteria:

- 1. Female subject who is pregnant, breastfeeding or is considering becoming pregnant during the study or for approximately 30 days after the last dose of study drug.
- 2. Recent (within 6 months prior to study drug administration) history of drug or alcohol abuse that could preclude adherence to the protocol in the opinion of the investigator.
- 3. Positive test result at Screening for hepatitis B surface antigen (HBsAg) or anti human immunodeficiency virus antibody (HIV Ab).
- 4. HCV genotype performed during screening indicating co-infection with more than one HCV genotype or if HCV genotype is indeterminate.
- 5. Requirement for and inability to safely discontinue the medications or supplements listed in Table 1 the protocol (Section 5.2.3.4) at least 2 weeks or 10 half-lives (whichever is longer) prior to the first dose of any study drug.
- Clinically significant abnormalities, other than HCV infection, that make the 6. subject an unsuitable candidate for this study in the opinion of the investigator, including, but not limited to:
 - Active or suspected malignancy.
 - Uncontrolled cardiac, respiratory, gastrointestinal, hematologic, neurologic, psychiatric, metabolic, or other medical disease or disorder, which is unrelated to the existing HCV infection.

- Uncontrolled diabetes as defined by a glycated hemoglobin (hemoglobin A1C) level > 8.5% at the Screening Visit.
- 7. Any cause of liver disease post transplantation other than chronic HCV infection including but not limited to the following:
 - Hemochromatosis
 - Alpha-1 antitrypsin deficiency
 - Wilson's disease
 - Autoimmune hepatitis
 - Alcoholic liver disease
 - Steatohepatitis on liver biopsy considered to be the primary cause of the liver disease rather than concomitant/incidental with HCV infection.
- 8. Clinical history of Fibrosing cholestatic hepatitis at any time post-transplant.
- 9. Screening laboratory analyses showing any of the following abnormal laboratory results:
 - ALT and AST > 10 × ULN
 - Albumin < 3.5 g/dL
 - Hemoglobin < 10 g/dL
 - Platelets < 70,000
 - Calculated creatinine clearance (using Cockcroft-Gault method) of
 30 mL/min
 - Direct bilirubin > 2 mg/dL
 - International Normalized Ratio (INR) > 1.5 ULN
- 10. Clinical history of acute renal failure in the 3 months prior to screening.
- 11. Re-transplantation of the liver or kidney.

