8.1.2.4 Subgroup Analysis

The percentage of ITT subjects with SVR₁₂ will be calculated, as will the corresponding two-sided 95% Wilson score confidence intervals for the following subgroups.

- HCV genotype (1, 2, 3, 4, 5, or 6) and subtype;
- Prior HCV treatment history;
 - For treatment-experienced subjects, type of non-response to previous treatment (on-treatment nonresponder or breakthrough, post-treatment relapse, or unknown/other);
- Prior sofosbuvir (SOF) experience (DAA naïve, SOF experienced);
- Organ transplant type (liver or kidney);
- IL28B genotype (CC or non-CC) and (CC, CT, or TT);
- Sex (male or female);
- Age ($< 65 \text{ or } \ge 65 \text{ years}$) and ($< 75 \text{ or } \ge 75 \text{ years}$);
- Race (White, Black/African-American, Asian, or other) and (black or non-black);
- Ethnicity (Hispanic or Latino, Not Hispanic or Latino);
- BMI ($< 25, \ge 25 \text{ to } < 30, \text{ or } \ge 30 \text{ kg/m}^2$);
- Baseline HCV RNA level (<6,000,000 or $\ge6,000,000$ IU/mL) and ($<2,000,000,\ge2,000,000$ to $<6,000,000,\ge6,000,000$ to <10,000,000, or $\ge10,000,000$ IU/mL);

[figure not shown]
- Baseline HOMA-IR ($< 2 \text{ or } \ge 2 \text{ mU} \times \text{mmol/L}^2$) and ($< 3 \text{ or } \ge 3 \text{ mU} \times \text{mmol/L}^2$);
- Baseline fibrosis stage (F0 F1, F2, F3, or F4 [if applicable]);
- Baseline platelet count (< $100 \text{ or } \ge 100 \times 10^9 / \text{L}$) and (< $120 \text{ or } \ge 120 \times 10^9 / \text{L}$);
- Baseline albumin (< LLN or \ge LLN);
- Baseline GGT (\leq ULN or > ULN);
- Baseline LDL ($< 88, \ge 88 \text{ to } < 119, \text{ or } \ge 119 \text{ mg/dL}$);
- Baseline APRI ($< 1 \text{ or } \ge 1$);
- Baseline FIB-4 ($< 1.45, \ge 1.45 \text{ to} \le 3.25, \text{ or} > 3.25$);
- Baseline AST/ALT ratio (< 1 or \geq 1);
- Geographic region (North America, Europe, Rest of world);
- Country (as appropriate);
- History of diabetes (yes/no);
- History of bleeding disorders (yes/no);
- History of depression or bipolar disorder (yes/no);
- History of cardiovascular disease (yes/no);
- Baseline metabolic syndrome (yes/no);
- Former injection drug user (yes, within last 12 months; yes, more than 12 months ago; or no);
- Subject on stable opiate substitution (yes/no);
- Presence of baseline resistance-associated variants (yes/no);
- Compliance to study drug (yes/no).

Further details about subgroup analysis will be described in the statistical analysis plan.

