4.3 Sample Size

It is planned to enroll approximately 90 subjects with a minimum of 15 post-renal transplant subjects and a maximum of approximately 50 subjects with HCV genotype 1 infection in this study. The primary efficacy endpoint of SVR₁₂ will be assessed for the ITT population. For the primary efficacy endpoint of SVR₁₂, with a sample size of 90 subjects and assuming that 96% of the subjects will achieve SVR₁₂, this study has

greater than 90% power to show non-inferiority to the historical SVR_{12} rate of 94% (based on the lower bound of a normal approximation of a single binomial proportion confidence interval being above a threshold of 86%) using a one-sample test for superiority using EAST 6.3.

The 86% threshold was established by applying an 8% non-inferiority margin to the historical SVR₁₂ rate of 94%

No adjustment for dropouts is applicable because subjects who do not have data at Post-Treatment Week 12 (after imputing) are counted as failures for SVR_{12} .

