6.1 Definition of Baseline and End of Treatment Assessment

6.1.1 Baseline

The baseline value refers to the last non-missing measurement collected before the first dose of study drug is received. The protocol specifies that all Day 1 assessments (other than optional intensive PK samples) are to be performed prior to administering the first dose of study drug. Therefore, all Day 1 assessments for which time is not collected will be assumed to be pre-dose and the baseline value will be the last non-missing measurement collected on or before the first day of study drug administration.

All Day 1 assessments with time available must be before the time of first dose to be considered baseline and the last non-missing measurement collected before the date and time of the first dose of study drug will be considered the baseline value. If multiple measurements that are prior to dosing are recorded on the same date and with the same time or if time is not available, then the average of these measurements will be considered the baseline value. The same baseline value will be used for analyses of the Treatment and Post-Treatment Periods.

Safety assessments that are related to a serious adverse event that occurred on the first dose day are excluded when applying this algorithm.

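### SAP Table 8 bounds Grade 1 albumin at 30 g/dL instead of 30 g/L, so the Grade 1 band is empty as written; a footnote on the 35 g/L albumin subgroup would also help

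*SAP*

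**What the plan says.** **Toxicity grading.** SAP 11.3.2 assigns toxicity grades from Table 8 and tabulates each subject's maximum grade. A post-baseline value counts only if its grade is worse than the baseline grade. The albumin row reads:

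- Grade 1: below LLN, down to 30 g/dL
- Grade 2: below 30, down to 20 g/L
- Grade 3: below 20 g/L
- Grade 4: none

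The hemoglobin row of the same table is in g/L throughout.

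**Albumin subgroup.** SAP 7.1 (baseline characteristics) and SAP 10.6 (efficacy subgroups) use the same split: "Baseline albumin (< 35 or" at least 35 g/L). Protocol 8.1.2.4 had cut it elsewhere: "Baseline albumin (< LLN or" at or above LLN). SAP 12.1 attributes its subgroup changes to consistency across the development program.

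**Entry limit.** Protocol 5.2.2, Criterion 9, excludes subjects on "Screening laboratory analyses showing any of the following abnormal laboratory results", and the list includes "Albumin < 3.5 g/dL".

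**Baseline.** SAP 6.1.1: "The baseline value refers to the last non-missing measurement collected before the first dose of study drug is received". Chemistry is drawn at Screening and again on Day 1 (Protocol Appendix C), so baseline is normally the Day 1 value.

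**Small subgroups.** Under SAP 10.6 the confidence interval "will be produced if there are at least 10 subjects in the subgroup".

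**The concern.** Table 8 is an operative rule. It decides which albumin values enter the maximum-grade counts. If one bound is in a different unit from the rest of its row, the printed rule and the intended rule give different tables. What is at stake is the Grade 1 albumin count: a zero produced by the unit slip would look like a finding that no subject had a mild decline.

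The subgroup raises a question of interpretation. When the cut equals the entry limit, the low group does not represent patients with low albumin. It consists of subjects who qualified and then had a lower value before dosing. The SAP's other laboratory cuts with a matching exclusion limit sit inside the eligible range: platelets have an exclusion limit of 70 and are split at 90 (× 10⁹/L), and creatinine clearance has a limit of 30 and is split at 60 and 90 mL/min. A reader who does not notice the coincidence for albumin could take the row for a comparison of low with normal albumin.

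**Working it through.** **1. Table 8 units**

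1 g/dL = 10 g/L.

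- Printed Grade 1 bound: 30 g/dL × 10 = 300 g/L.
- Grade 2 upper bound in the same row: 30 g/L.
- Ratio: 300 / 30 = 10.

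As printed, Grade 1 requires albumin below LLN and at least 300 g/L. The documents do not give LLN, but the band is empty for any LLN under 300 g/L. Values of at least 30 g/L and below LLN are not Grade 2 either, since that starts below 30 g/L. They have no grade.

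With the bound at 30 g/L, Grade 1 runs from LLN down to 30 g/L and Grade 2 from below 30 to 20 g/L. The bands meet with no gap or overlap.

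**2. What the slip changes**

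- *Grade 1 albumin count:* zero if coded literally.
- *Grade 2 and Grade 3 counts, the count of at least Grade 3, and the listing of increases to Grade 2 or higher:* unchanged. A baseline between 30 g/L and LLN would be ungraded instead of Grade 1, but a later Grade 2 or 3 value is worse than either.
- *Mean change from baseline by visit (SAP 11.3.2) and shifts against the normal range (Protocol 8.1.5.2):* unchanged, as neither uses Table 8.

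**3. The subgroup cut**

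3.5 g/dL × 10 = 35 g/L, identical to the cut in SAP 7.1 and 10.6. A subject enrolled per protocol, including one who qualified on a retest (Protocol 5.1.1.1), is in the low group only if a later pre-dose value is below 35 g/L. A subject dosed in breach of Criterion 9 stays in the ITT population (SAP 5.1.1) and could also fall there.

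**4. How large the low group might be**

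SAP 4.3: "It is planned to enroll approximately 90 subjects". A confidence interval needs 10 / 90 = 11.1% of them in the low group. The documents give no share, so it has to be assumed. With share d, the expected count is 90d and the chance of an interval is P(X ≥ 10) for X ~ Binomial(90, d):

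| Assumed share d | Expected count | Chance of at least 10 |
|---|---|---|
| 2% | 1.8 | 0.001% |
| 5% | 4.5 | 1.5% |
| 10% | 9.0 | 41% |
| 15% | 13.5 | 88% |

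A rough model for d takes Screening and Day 1 values as a normal subject mean plus independent normal within-subject variation, and computes P(Day 1 < 35 given Screening ≥ 35). All inputs are assumptions: between-subject SD 3–4 g/L and within-subject SD 1.5–2.0 g/L.

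- Mean 40–42 g/L: d = 1.1% to 6.2%, or 1.0 to 5.6 of 90; chance of at least 10 is at most about 5%.
- Mean 38 g/L: about 7 to 10 of 90; chance of at least 10 is about 20% to 55%.

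**5. Would another cut be informative?**

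At the planned 96% SVR12, expected failures are 90 × 0.04 = 3.6, about 4. With a 45/45 split and all 4 failures on one side, the two-sided Fisher p-value is 2 × C(45,4) / C(90,4) = 2 × 148,995 / 2,555,190 = 0.117. Even the most extreme allocation does not reach 0.05.

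**The case against.** **On Table 8.** The intended unit is plain from the Grade 2 cell beside it, and a careful programmer would probably code 30 g/L without asking. That is true, and it keeps the point small. It does not remove the point, because the SAP is meant to guide programming and the cell is wrong as printed.

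A reader might infer that mild albumin declines would disappear from the safety report. The documents do not support this: mean changes and shift summaries would still show them, and only the Grade 1 count is exposed. Nor can one say that every subject starts at 35 g/L or more. Criterion 9 applies at Screening, whereas grading is relative to a baseline normally taken on Day 1, which can be lower.

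**On the subgroup.** The analysis is descriptive, the SAP already withholds intervals for groups under 10, and program-wide consistency is a stated reason for the subgroup changes. A reader might infer that the low group must be empty, must stay below 10, or must be re-cut. None of these follows:

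- The group is not empty by construction.
- Its size depends on an albumin distribution that the documents do not give; at an assumed mean of 38 g/L it could reach 10.
- Calling its members mostly day-to-day variation goes too far. Enrolment may follow Screening by up to 42 days, and SAP 11.3 admits both central and local laboratory values.
- With about 4 expected failures, moving the cut would not show whether response depends on albumin. A new cut would be a preference, and a median cut would be data-driven.

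What stands is that the cut equals the entry limit and the SAP does not say so.

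**Conclusion.** The Table 8 error is certain and needs no assumption beyond an LLN under 300 g/L. The Grade 1 albumin bound is ten times too high as printed, the band is empty, and values from 30 g/L to LLN are ungraded. The effect is confined to the Grade 1 albumin count.

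The subgroup remark is optional. That the two limits coincide is a fact. That the low group will be small is likely, not established, because every size above rests on assumed albumin values. Neither matter affects the primary or secondary efficacy analyses, and the whole point is minor.

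**What to change.** 1. In SAP Table 8, albumin row, change the Grade 1 bound from 30 g/dL to 30 g/L, and check that the programmed bound and the units of the albumin data agree with it.
2. Optionally, add a footnote to the albumin rows produced under SAP 7.1 and 10.6: the cut equals the Criterion 9 limit, so, apart from eligibility deviations, subjects below 35 g/L are those whose pre-dose value fell after they qualified. The cut can stay where it is.

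The cost is one unit and one sentence, with no new data and no change to any efficacy analysis.

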10.7 Additional Efficacy Analyses

The following additional efficacy endpoints will be summarized:

- The percentage of subjects with HCV RNA < LLOQ at each post-baseline visit in the Treatment Period (using data as observed);
- The percentage of DAA-naïve subjects with on-treatment virologic failure;
- The percentage of DAA-naïve subjects with post-treatment relapse;
- The percentage of subjects with SVR₄;
- The percentage of subjects with SVR₂₄;

- The percentage of subjects who relapsed after achieving SVR₁₂ (**Relapse₂₄**);
- The percentage of subjects with virologic failure through Post-Treatment Week 12 (i.e., the SVR₁₂ non-responders due to on-treatment virologic failure or Relapse₁₂)

In the above analyses for SVR, virologic failure, and relapse, the percentage of subjects with a two-sided 95% Wilson score interval will be summarized. Imputations for missing data will be performed as described in Section 6.3 for analysis of SVR, where a missing response will be imputed as a failure after performing the described imputation. All other endpoints will be presented using data as observed.

A summary of the subjects who completed treatment and relapsed (defined as **Relapse_{overall}**) will be prepared displaying the number of subjects relapsing overall and by SVR visit window (within the SVR₄, SVR₁₂, SVR₂₄ windows or after SVR₂₄ window), including the subject number and the SVR visit window corresponding to the first occurrence of relapse. A similar listing will be prepared for subjects who prematurely discontinued treatment and relapsed after having HCV RNA < LLOQ at their Final Treatment Visit.

The number and percentage of subjects who do not achieve SVR_{12} will be summarized by reason for non-response (as defined in Section 10.1). A listing of subject numbers and reason for non-response will be prepared. A similar summary and listing will be prepared for subjects who do not achieve SVR_{24} .

The concordance between SVR_{12} and SVR_{24} will be assessed by the agreement between SVR_{12} and SVR_{24} and the positive predictive value (PPV) and negative predictive value (NPV) of SVR_{12} on SVR_{24} . The agreement between SVR_{12} and SVR_{24} is a percentage defined as the number of subjects achieving both SVR_{12} and SVR_{24} and the number of subjects where both SVR_{12} and SVR_{24} are not achieved. The PPV of SVR_{12} on SVR_{24} is the proportion of subjects who achieve SVR_{12} and SVR_{24} out of all subjects who achieved SVR_{12} . The NPV of SVR_{12} on SVR_{24} is the proportion of subjects who achieved

 SVR_{12} nor SVR_{24} out of all subjects who did not achieve SVR_{12} . Similarly, the concordance between SVR_4 and SVR_{12} will be summarized.

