5.4.1.1 Virologic Failure Criteria

[figure not shown]
The following criteria will be considered evidence of HCV virologic failure for the purposes of subject management:

- Confirmed increase from nadir in HCV RNA (defined as 2 consecutive HCV RNA measurements of > 1 log₁₀ IU/mL above nadir) at any time point during study drug treatment.
- Confirmed HCV RNA ≥ 100 IU/mL (defined as 2 consecutive HCV RNA measurements ≥ 100 IU/mL) after HCV RNA < LLOQ during study drug treatment.

When confirmatory testing is required, it should be completed as soon as possible and the subject should remain on study treatment until the virologic failure criteria has been confirmed. Subjects meeting the virologic failure criteria will be discontinued from study drug and will continue to be followed in the Post-Treatment Period for the emergence and persistence of resistant viral variants until 24 weeks post-treatment.

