6.2 Definition of Analysis Windows

For efficacy analyses of HCV RNA and resistance, the time windows specified in Table 1 and Table 2 describe how efficacy data are assigned to protocol-specified time points during the Treatment and PT Periods, respectively. All time points and corresponding time windows are defined based on the date/time of blood sample collection.

For laboratory data vital signs and PRO measurements, the time windows specified in Table 1 and Table 3 describes how data are assigned to protocol specified time points.

If more than one assessment is included in a time window, the assessment closest (except in analyses of SVR) to the nominal time will be used. If there are two observations equally distant to the nominal time, the latest one will be used in analyses. For analyses of SVR (e.g., SVR₁₂), the last value in the window will be used.

If multiple measurements are made on the same day for a safety laboratory parameter or a vital sign parameter, the average of the values will be used to calculate descriptive statistics and in analyses of the mean change from baseline. For summaries of shifts from baseline and potentially clinically significant values, multiple values on the same day will not be averaged; all values will be considered for these analyses.

Scheduled Visit	Nominal Day (Study Day)	Time Window (Study Day Range)	
Day 1/Baseline ^a	1	$\leq 1^a$	
Day 3	3	2 to 5	
Week 1	7	6 to 8	
Day 10	10	9 to 12	
Week 2	14	13 to 21	
Week 4	28	22 to 42	
Week 6	42	43 to 49	
Week 8	56	50 to 70	
Week 12	84	71 to 98	
Final Treatment Visit ^b	2 to \leq 2 days after	2 to \leq 2 days after last dose of study drug	

Table 1.Analysis Time Windows for HCV RNA, Resistance Endpoints,
Laboratory, Vital Sign Measurements and PRO Instruments
(Treatment Period)

a. Day of first dose of study drug.

b. The last value within the window will be used to define the Final Treatment Visit value. The upper bound of this Final window is Study Drug End Day ≤ 2 .

Note: Data must also have Study Drug End Day ≤ 2 for all windows. The result closest to the scheduled time point will be used. PRO instruments are collected at Day 1 and End of Treatment Visit (Week 12) only.

Table 2.Analysis Time Windows for HCV RNA and Resistance Endpoints
(Post-Treatment Period)

Scheduled Visit ^a	Nominal Day (Study Drug End Day)	Time Window (Study Drug End Day Range)
Post-Treatment Week 2	14	3 to 21
Post-Treatment Week 4	28	22 to 42
Post-Treatment Week 8	56	43 to 70

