6.3 Missing Data Imputation

Missing Data Imputation for SVR

HCV RNA values will be selected for analysis based on the analysis windows defined in Section 6.2.

For analyses of SVR, subjects missing visit values will have backward imputation applied, if possible. For backward imputation, if the nearest HCV RNA value after the SVR window is unquantifiable or undetectable, then it will be used to impute the HCV RNA value in the SVR window. If a subject is missing an HCV RNA value within the appropriate SVR window after performing backward imputation, then this value will be imputed with an HCV RNA value from a local laboratory if present; otherwise, the HCV RNA value will be missing. Subjects with missing HCV RNA data in the analysis window, after imputations, will be imputed as a failure.

Regardless of the imputation method described above, if a subject starts another treatment for HCV, then all HCV RNA values for this subject measured on or after the start date of the new HCV treatment will be excluded from analyses. The subject will be considered a failure for summaries of viral response at all time points after the start of the new HCV treatment.

Missing Data Imputation for Virologic Failure

If HCV RNA values from the central laboratory are missing but a local laboratory value is present in the appropriate time period, then the local laboratory value will be used to assess post-treatment relapse and on-treatment virologic failure.

Missing Data Imputation for PRO Questionnaires

The handling of missing data for patient reported outcomes (PROs) will be as follows. If a respondent answers at least 50% of the items in a multi-item scale of the SF-36v2, the missing items will be imputed with the average score of the answered items in the same scale. In cases where the respondent did not answer at least 50% of the items, the score for that domain will be considered missing. The Mental and Physical Component Summary measures will not be computed if any domain is missing. The missing items of the FSS questionnaire will be imputed with the average score of the answered items as long as more than 50% of the items on the FSS are answered. For EQ-5D-3L index and VAS scores, no imputation will be performed for missing items.

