10.0 Efficacy Analysis

10.1 General Considerations

General Considerations

All efficacy analyses will be performed on the ITT population, unless otherwise specified.

Missing data will be imputed as described in Section 6.3 for analyses of the HCV RNA endpoints of SVR.

Plasma HCV RNA levels will be determined for each sample collected by the central laboratory using the Roche COBAS[®] AmpliPrep/COBAS[®] TaqMan[®] HCV Quantitative Test, v2.0. The lower limit of detection (LLOD) and lower limit of quantification (LLOQ) for this assay (regardless of genotype) are both 15 IU/mL.

HCV RNA results that are detectable but not quantifiable are reported as "< 15 IU/ML HCV RNA DETECTED" and those that are undetectable are reported as "HCV RNA NOT DETECTED" in the database.

The notation "HCV RNA < LLOQ" is used to represent all HCV RNA values < 15 IU/mL, including values reported as "HCV RNA NOT DETECTED" or "< 15 IU/ML HCV RNA DETECTED." HCV RNA ≥ LLOQ are all quantifiable values of 15 IU/mL or greater.

Definitions for Efficacy Endpoints

A confirmed quantifiable value during treatment is defined as any two consecutive HCV RNA measurements \geq LLOQ (or 100 IU/mL for **Breakthrough**), either both during treatment or at the final treatment measurement and the next consecutive post-treatment measurement. A confirmed quantifiable post-treatment value is defined as any two consecutive post-treatment HCV RNA measurements \geq LLOQ.

Breakthrough = confirmed HCV RNA \geq 100 IU/mL after HCV RNA < LLOQ during the Treatment Period; or confirmed increase from nadir in HCV RNA (two consecutive

HCV RNA measurements > 1 \log_{10} IU/mL above nadir) at any time point during the Treatment Period. A single breakthrough value (≥ 100 IU/mL or > 1 \log_{10} above nadir) followed by lost to follow-up also will be considered a breakthrough (i.e., will not require confirmation).

EOT failure = HCV RNA \geq LLOQ at end of treatment with at least 6 weeks of treatment, where the HCV RNA value must be collected on or after Study Drug Day 36 and study drug duration \geq 36 days.

On-treatment virologic failure = Breakthrough or **EOT failure**.

 $SVR_4 = HCV RNA < LLOQ$ in the SVR_4 window (4 weeks after the last actual dose of study drug) without any confirmed quantifiable ($\geq LLOQ$) post-treatment value before or during that SVR window.

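### The by-visit HCV RNA < LLOQ rate in SAP 10.7 drops subjects who failed and stopped drug earlier, so a late-visit rate can be overstated by up to the proportion who failed

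*SAP*

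**What the plan says.** The endpoint is "The percentage of subjects with HCV RNA < LLOQ at each post-baseline visit in the Treatment Period (using data as observed") in SAP 10.7, and Protocol 8.1.2.5 lists the same one for the ITT population. SAP 10.7 limits counting missing as failure to SVR and adds: "All other endpoints will be presented using data as observed".

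Other rules decide who still has a value at a given visit:

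- Protocol 5.4.1.1: "Subjects meeting the virologic failure criteria will be discontinued from study drug". Before that, "the subject should remain on study treatment until the virologic failure criteria has been confirmed".
- SAP 6.2, note to Table 1: "Data must also have Study Drug End Day ≤ 2 for all windows". Day 0 is the day of the last dose.
- SAP 6.3, on subjects who start another HCV therapy: "The subject will be considered a failure for summaries of viral response at all time points after the start of the new HCV treatment". This sits in the part of 6.3 that deals with SVR.
- SAP 6.2, Table 1, also defines a Final Treatment Visit: "The last value within the window will be used to define the Final Treatment Visit value".

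SAP 10.1 defines on-treatment virologic failure as breakthrough or EOT failure, the latter being HCV RNA at or above "LLOQ at end of treatment with at least 6 weeks of treatment". SAP 10.4 reports it as a secondary endpoint.

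**The concern.** As-observed summaries are usually defended on the ground that missing values are incidental. Here the protocol itself creates the gap. A confirmed failure ends dosing, later samples fall outside every Treatment Period window, and the subject is absent from later denominators although the outcome is known. The resulting error can only raise the rate.

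The plan also treats like cases differently. Under SAP 6.3 a subject who fails and is re-treated counts as a failure in summaries of viral response from then on, if that rule reaches this table at all. A subject who fails in the same way and is not re-treated simply disappears.

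What is at stake is how the on-treatment response table reads. The report could show several on-treatment failures in one table and, in another labelled ITT, a Week 12 suppression rate that leaves them out.

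**Working it through.** **The plan's own figure.** The documents give no planned value for this endpoint. The nearest figure is the SVR12 power in Protocol 8.2 and SAP 4.3: above 90% with N=90, a true rate of 96% and a threshold of 86%. With the null variance in the critical value, the standard errors are √(0.86×0.14/90)=0.0366 and √(0.96×0.04/90)=0.0207. Then (0.10−1.96×0.0366)/0.0207≈1.37, which gives 91.5%. The exact calculation needs at least 83/90 responders and gives 97.2%. The stated power is reproduced, and nothing below depends on it.

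**Inputs.** N=90 (Protocol 8.2). The Week 12 window is Study Day 71 to 98, with no value more than 2 days after the last dose (SAP Table 1). F is the number of on-treatment failures. Of these, e are off drug before the window with no value in it, and F−e are quantifiable within it. F and e are assumptions, because the documents give no on-treatment failure rate for this population. All other subjects are taken as suppressed, other missing data are ignored, and each sample is taken to fall in the window of its own visit.

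**Formulas.**

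- As observed: (90−F)/(90−e)
- Failures retained: (90−F)/90
- Overstatement: (90−F)·e / [90·(90−e)]

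The overstatement rises with e, from 0 at e=0 to F/90 at e=F.

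**Week 12 results.**

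| F | e | As observed | Retained | Overstatement (points) |
|---|---|---|---|---|
| 1 | 1 | 89/89 = 100% | 98.9% | 1.1 |
| 1 | 0 | 89/90 = 98.9% | 98.9% | 0 |
| 5 | 5 | 85/85 = 100% | 94.4% | 5.6 |
| 5 | 3 | 85/87 = 97.7% | 94.4% | 3.3 |
| 5 | 0 | 85/90 = 94.4% | 94.4% | 0 |
| 10 | 10 | 80/80 = 100% | 88.9% | 11.1 |
| 10 | 5 | 80/85 = 94.1% | 88.9% | 5.2 |
| 10 | 0 | 80/90 = 88.9% | 88.9% | 0 |

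**Paths over visits.**

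- Five failures first quantifiable at Week 4 and confirmed at Week 6 give 85/90=94.4% at both visits. Weeks 8 and 12 then read 85/85=100%, against 94.4% with failures retained.
- Two new failures at each of Weeks 4, 6, 8 and 12 (F=8), each confirmed at the next scheduled visit, give 97.8%, 95.6%, 95.5% and 82/86=95.3%. If each is confirmed before the next visit, the series is 97.8%, 97.7%, 97.7% and 82/84=97.6%. With failures retained it is 97.8%, 95.6%, 93.3% and 82/90=91.1%. The Week 12 overstatement is 4.2 or 6.5 points.

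**The case against.** A reader might infer that the late-visit rate returns to about 100% however many subjects fail, or that it can only recover after each failure. The documents do not support either reading. Subjects stay on drug until failure is confirmed, so their quantifiable values count up to that point. The premature discontinuation visit is due within 2 days of the last dose (Protocol 5.4.1) and includes an HCV RNA sample (Appendix C), so that value can count too. Subjects quantifiable at Week 12, including EOT failures treated to that visit, count in its window. A low-level rebound below 100 IU/mL need not meet the stopping criteria, so such a subject can remain in the denominator as not suppressed. New failures lower the rate, as the second path shows.

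It is also fair to say that failures are reported elsewhere: as a secondary endpoint with Wilson intervals, among the reasons for SVR12 non-response, and in subject listings. The by-visit rate is descriptive, its as-observed basis is stated in both documents, and it answers a different question from cumulative failure. The only virologic failure count in the documents, 1 of 79 non-cirrhotic GT1 subjects in Phase 2b (Protocol 5.6.4.2), would scale to 90×1/79≈1.1 subjects. That count was not in transplant recipients and is not specific to on-treatment failure, but it gives no support for a large effect. All this limits the importance of the point. It does not put the missing failures back into the late-visit rows.

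The Final Treatment Visit value in Table 1 does retain discontinued failures. However, Protocol 8.1.5.2 and 8.1.5.3 name that visit for laboratory and vital-sign summaries, while Protocol 8.1.2.5 and SAP 10.7 do not name it for HCV RNA. Even if shown, it would not correct the Week 8 and Week 12 rows.

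Finally, retaining virologic failures while leaving other gaps as observed makes the table a hybrid. That is a real cost, but defensible: for these subjects the response status is known.

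**Conclusion.** The point holds as a minor defect in a descriptive table. The as-observed rule, the window limit and mandatory discontinuation together remove earlier failures from later denominators, and the error is upward only. Its size lies between 0 and F/90. The rate reads 100% only if every failure was off drug before the window and everyone else observed is suppressed. These figures rest on N=90, on assumed numbers and timing of failures, and on no other missing data.

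No primary or secondary conclusion changes. SVR12 counts missing data as failure after the imputations in SAP 6.3, and on-treatment virologic failure is counted directly. Nothing here questions the stopping rule itself.

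**What to change.** In SAP 10.7:

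1. State that a subject who has met the SAP 10.1 definition of on-treatment virologic failure stays in the denominator as not < LLOQ at all later Treatment Period visits, with other missing values left as observed.
2. Show n/N at each visit, so that any change in the denominator is visible.
3. State whether the rule in SAP 6.3 on starting new HCV treatment applies to this table.

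The failure definition already exists, so the cost is a few SAP sentences and one programming rule. The downside is that late-visit rates become slightly less favourable and the table is no longer purely as observed, which its title or footnote should say.
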